Psychological Interview: There is a possibility that a patient may become distressed when being asked about symptoms or personal information during the diagnostic evaluation or assessment session. The primary risks to the patients are discomfort or anxiety. Subjects may also experience some discomfort or anxiety from discussing personal information. Yet this anxiety is not expected to be greater than that subjects already experience and subjects will be assured that they will be able to withdraw from the study at any time. There is a possibility of suicidal ideation as a result of any anxiety or distress associated with discussing personal information. This risk is largely reduced by screening out patients with significant suicidal ideation or those who have enacted suicidal behaviors within 6 months prior to intake.

Cognitive Tests: The cognitive tasks pose no risks to participants. The tasks will require sustained attention and mental effort for a steady period of time. This could lead to minor temporary fatigue or boredom, but otherwise there are no known risks. We will ensure that data remain as confidential as possible. Also, these data generally are not considered to be of sensitive nature.

Confidentiality: Although every effort will be effort made to assure confidentiality, it is possible someone could without permission gain access to study related data during the time they are being used or stored for examination results.

Blood draw: Temporary irritation from the needle stick, the likelihood of pain or bruising at the site of the blood draw, occasional symptoms of lightheadedness, and, in rare cases, infection at the site of the blood draw are all risks and discomforts associated with the blood draw procedure.

SS-OCTA: OCTA is painless and safe techniques that will be used to investigate the structure and function of the retina. Performing these imaging techniques in individuals with psychotic disorders does not pose specific, additional unique challenges or risks to the participants. Participants will have their pupils dilated for OCT/OCTA retinal imaging, as is done with all ophthalmology imaging facilities, which may result in light sensitivity or acute angle-closure glaucoma. When possible, we will forgo pupil dilation, especially when high quality retinal images can be obtained without the need for pupillary dilation.

IV infusion of SNP:

IV treatment is relatively safe, there can be complications if not administered properly. The most common complications include phlebitis, extravasation, air embolism, infection.

The single administration of IV Sodium nitroprusside has been reported to be safe and well tolerated. The most important adverse reactions are the avoidable ones of hypotension and cyanide toxicity and other side effects reported as; bradycardia, tachycardia, palpitations, headache, increased intracranial pressure, skin rash and nausea. The potential for cyanide toxicity

is greatest when more than 500 g/kg of sodium nitroprusside is administered faster than 2 g/kg/min, as cyanide is generated faster than the unaided patient can eliminate. Cyanide toxicity will be avoided in this study as the dose administered is very low, and individuals with renal impairment will be excluded. Also, the study treatment will be infused within 3-12 hours of preparation as sodium nitroprusside is only stable in solution for 24 hours. The infusion protocol will be 0.5mcg/kg/min which is the minimum therapeutic dose and patients will be continuously monitored during the infusion. The infusion procedure will take place at the Clinical Research Center at BIDMC, which is a fully staffed center with nurses and physicians, as well as all the necessary monitoring and personal protective equipment. In 4 other similar studies with the same protocol, there were no serious side effects.

Sodium nitroprusside does have some potential for drug-drug interactions. The hypotensive effect of sodium nitroprusside is augmented by that of most other hypotensive drugs, including ganglionic blocking agents, negative inotropic agents, and inhaled anesthetics. Subjects taking any of these drugs will be excluded from the study. Patients will also be advised not to take these medications during the study¹⁻⁴.

Protections Against Risks

Protection against potential clinical risks: All research procedures and assessments will be completed by trained and experienced personnel. We also strive to make the assessments as free from burden as possible. Assessments will be scheduled at the convenience of subjects, and we also arrange for transportation and parking. The research staff will be regularly in touch with the participants during participation and will encourage them to contact a 24-7 number in the event of an emergent need. If the participant develops worsening of symptoms, they will be referred for treatment as appropriate.

Protection for risks associated with retinal imaging: Oversight of this study will come from local IRBs. Subjects will be screened for exclusionary criteria, which include retinal diseases and past adverse effects from ophthalmic medication used for pupil dilation. Participants will also be provided with disposable sunglasses and asked to avoid driving and operating other potentially dangerous equipment for 2 hours after pupil dilation. In the event of an adverse effect from the medication for pupil dilation, there will be clinical staff (including my collaborators, Drs [name]) available to the participant at the Retinal Imaging site (Mass Eye and Ear) to promptly assess and treat the participant.

Protection against potential risks with SNP administration: All participants will undergo a physical examination (PE), routine laboratory tests (CMP, CBC, CRP, TSH, Lipid panel), urine toxicology tests and 12-lead-electrocardiogram to ensure medical stability. To monitor safety and tolerability, participants will also be administered the Abnormal Involuntary Movement Scale, the Systematic Assessment for Treatment Emergent Effects (SAFTEE), and the Columbia-Suicide Severity Rating Scale prior to each infusion, after each infusion, and at follow-up. Hypotension is unavoidable with this medication, but participants will be continuously monitored to avoid any potential complications and there will be nursing available to help address any potential complications by stopping the infusion and/or administrating fluids to help increase a patient's blood pressure. Cyanide toxicity will be avoided by providing low dosages of SNP to participants, which avoids this risk.

References:

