NCT Number: NCT04986072

Official Title: Sodium Nitroprusside in Early Course Schizophrenia

Document Type: Study Protocol and SAP

Document Date: 07/17/2023

PART B STUDY DESCRIPTION

Title of Protocol	Proof of Mechanism Study using a Retinal Biomarker to Predict Treatment Response with Intravenous Sodium Nitroprusside in Symptomatic Early Course Schizophrenia
Principal Investigator	[name]

B1. PURPOSE OF PROTOCOL

- 1. The main purpose of this proposal is to determine the effectiveness of a single intravenous administration of sodium nitroprusside (SNP) (0.5 mcg/kg/min for 4 hours) on positive and negative symptoms in symptomatic Early Course Schizophrenia (ECS).
- 2. To examine the effect of SNP on cognition and retinal imaging phenotypes in ECS, and whether baseline retinal microvasculature or inflammation (CRP levels) correlate with a change in psychosis symptoms or cognition.

We hypothesize that SNP will improve psychosis symptoms and cognition in symptomatic ECS and that this change can be predicted by retinal vessel morphology or CRP levels. We predict that SNP will improve oxygen supply and reduce inflammation, which will be evidenced by reductions in retinal vessel phenotypes.

B2. SIGNIFICANCE AND BACKGROUND FOR THE STUDY

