SS-OCTA: Images will be obtained using the Zeiss PLEX Elite 9000, which is a quick, inexpensive, and non-invasive method for acquiring retinal images with an axial resolution of ~5µm and a scan depth of 3.0mm. Automated layer segmentation provides four horizontal depth-resolved retinal slabs: superficial (SRL), deep (DRL), outer retinal layer (ORL) and the choriocapillaris. Participant images will be excluded for low signal strength (≤6), blink artifacts, doubling artifacts, media opacity obscuring visualization of the vasculature, and/or segmentation errors. Manual segmentation editing will be conducted to ensure proper layer assessment. Microvessels for the SRL, DRL, and choriocapillaris slab will be processed using a custom semiautomated algorithm we developed to rapidly quantify several vessel parameters including vessel density, length, diameter, and capillary network. All images will be independently analyzed and compared among study subjects by two graders blinded to the group assignment.

Outcome: Primary outcomes include the change in PANSS positive and negative scores (2hrs, 5hrs, 1wk, 2wk, and 4wks) in the SNP group compared to placebo. The secondary outcomes include the change in overall cognition (0hr, 1wk, 2wk, and 4wks) and retinal microvascular measures (0hr, 5hrs), as well as examining the relationship between baseline or change in retinal vessel measures or CRP and the change in psychosis symptoms and cognition after SNP treatment compared to placebo.

SNP Treatment Protocol

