- All side effects and vital parameters will be recorded during the infusion and 2 hours following the infusion by CRC nursing.
- Any abnormal, clinically significant vital signs will be recorded as adverse events.

Discharge Procedure

- Gross motor and cognitive function, ataxia, reflexes/clonus will be evaluated and documented by a study PI ([name]) prior to discharge.
- Before being discharged patients should be awake and alert, feeling well, with no nausea, vertigo, or dizziness.
- There should be no significant change in vital signs from prior to infusion.
- They will be given a small meal before discharge from the CRC.
- Patients will be instructed not to drive. If necessary, the study nurse will release them to the
 care of an adult family member or caregiver, who will accompany the patient home. If
 needed, a trained Research Assistant will contact the participants support system to ensure
 transportation is coordinated.

Study Drug Handling

- Nitroprusside will be compounded by research pharmacy in 5% dextrose
- 5% dextrose will be used as placebo
- Study drug will be stored at room temperature and the required amount will be released from the pharmacy to the CRC at the time a patient is scheduled for the protocol.
- Study drug will be provided in light-blocked bags with labeling to ensure blinding of study staff.

Nitroprusside standard concentration is 50mg/250mL of D5W and the concentrated version is 100mg/250mL.

Institutional Approvals

Critical Care Executive – [name] and [name] – Approval granted on 9/8/21 Critical Care Practice – [name] and [name] – Approval granted on 9/8/21

B. Statistical Considerations

Power calculation: With 16 ECS individuals in the SNP group and 16 in the placebo group we will have >80% power to detect a 10-point PANSS difference between the placebo and treatment groups, with a SD of 6, alpha of 0.05, 2-sided alternative hypothesis, 2-sample t-test, based on the sample size suggested by the retinal vessel differences in our pilot data. The above-mentioned sample size was determined based on our pilot SS-OCTA data, which suggests that we will have >70% power to detect group differences of at least 0.007 (estimated standard deviations of skeletal density =0.008, significance level=0.05, two-sided t-tests).

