Baseline demographic details will be compared between the SNP and placebo groups using independent-samples t tests or Mann-Whitney U tests where appropriate using R software. Categorical data will be compared using chi-square tests. Effect sizes will be provided using Cohen's d. The primary outcome (PANSS) will be analyzed using a 2 (treatment group) × 5 (time point) mixed analysis of variance (ANOVA). Analyses of secondary outcome measures will be compared using a 2-group x 4 time point mixed ANOVA for cognition and a 2 x 2 for retinal measures. The relationship between baseline or change in retinal vessel measures or CRP and change in PANSS scores or cognition will be performed using Pearson's (parametric) or Spearman's (non-parametric) correlation.

C. Subject Selection

Population: Men and women, 18-60 years of age, from diverse background, symptomatic, with early course schizophrenia, and meet all study inclusion and exclusion criteria.

Inclusion criteria for ECS patients are: a DSM-V diagnosis of SZ or schizoaffective disorder with ≤5 years from the onset of psychosis and up to 2 years of lifetime exposure to antipsychotics, total score of ≥55 on the PANSS with a score of ≥3 on 1 or more PANSS Positive Scale items (delusions, conceptual disorganization, hallucinatory behavior, suspiciousness, or unusual thought content) and/or score of ≥3 on the CGI-S scale, taking antipsychotic for 8 weeks with a stable dose of 4 weeks (no medication change will be allowed during the trial), English proficiency, understands and is able, competent and willing to give informed consent in accordance with the International Conference on Harmonization Good Clinical Practice Guidelines.

Exclusion criteria are:

- Presence of renal, hepatic, cardiac, hematologic, neurologic impairments or abnormal physical exam.
- Presence of retinal disease (myopia >4.0 diopters)

- Baseline systolic BP <100mmHg or symptomatic orthostatic hypotension (systolic BP <90 mmHg or diastolic BP <60 mmHg) with any of the following: lightheaded or dizzy, blurry vision, weakness, syncope, confusion, nausea.
- Pregnant or breastfeeding (pregnancy test at screening visit and prior to randomization).
- Abnormal laboratory testing (see appendix)
- Treatment with medications that may interfere with the metabolism or excretion of SNP or are associated with drug-drug interactions (see list of medications below).
- Prior history of intolerance to SNP
- Currently taking clozapine or chlorpromazine

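### The plan names two primary PANSS subscales but not which score, ANOVA effect or success rule decides, so the false positive rate of the primary claim is not held at 5%

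*Combined protocol and SAP*

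**What the plan says.** The combined protocol and SAP describes the primary outcome in four places.

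- **B1, Purpose of Protocol.** The main aim is effectiveness "on positive and negative symptoms in symptomatic Early Course Schizophrenia (ECS"). Both domains are named.
- **B3.A, Outcome.** "Primary outcomes include the change in PANSS positive and negative scores", with times "2hrs, 5hrs, 1wk, 2wk, and 4wks) in the SNP group compared to placebo". That makes two scores at five times each, with no time singled out.
- **B3.B, Power calculation.** "With 16 ECS individuals in the SNP group and 16 in the placebo group" are said to give ">80% power to detect a 10-point PANSS difference between the placebo and treatment groups", with SD 6 and "alpha of 0.05, 2-sided alternative hypothesis, 2-sample t-test". The text does not say whether the 10 points are on the positive, negative or total score.
- **B3.B, analysis paragraph.** "The primary outcome (PANSS) will be analyzed using a 2 (treatment group) × 5 (time point) mixed analysis of variance (ANOVA"). The outcome is now singular, and neither the score nor the deciding effect is named.

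Alpha for PANSS appears only in the power calculation. There is no alpha split, testing order, either/both rule or decisive time point anywhere in the document. B3.A calls the trial a pilot.

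**The concern.** A 5% error rate belongs to a defined claim: one score, one contrast, one rule for success. Here the outcome section gives two scores, the analysis paragraph gives one unnamed score, and a mixed ANOVA yields at least two tests that could carry a treatment claim (group, and group by time). The power calculation uses a two-sample t-test, which is neither of these ANOVA tests as such and does not say which contrast is meant.

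With these choices open, several 5% tests could each support a statement that SNP works, and the text would not rule any of them out. The background section describes the earlier clinical results as mixed. In that setting, one significant subscale or one significant interaction is easy to over-read.

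**Working it through.** **Inputs from the plan (B3.B):** 16 per arm, difference 10, SD 6, two-sided alpha 0.05. **Assumed, not in the plan:** the correlation between the two subscale tests (shown over a range) and, in the ANOVA simulation, a correlation of 0.6 between time points.

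**1. The plan's own power figure.** d = 10/6 = 1.667. Noncentrality = d × √(n/2) = 1.667 × √8 = 4.714, with 30 degrees of freedom.
- Exact noncentral t: power 99.5%.
- Normal approximation: Φ(4.714 − 1.960) = Φ(2.754) = 99.7%.

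The claim of more than 80% is true as a lower bound. It covers one t-test on one score.

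**2. What is defined and what is not.**

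| Element | B3.A Outcome | B3.B Power | B3.B Analysis |
|---|---|---|---|
| Score | positive and negative | unspecified PANSS | unspecified PANSS, singular |
| Effect tested | change, SNP vs placebo | difference, t-test | group or group × time not stated |
| Time | five, none decisive | none | five, none decisive |
| Alpha | none | 0.05, undivided | none |
| Either or both | not stated | not stated | not stated |

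**3. One 0.05 test per subscale, success on either.** If independent: 1 − 0.95² = 9.75%. For correlation r, the rate is 1 − P(|Z₁| < 1.96 and |Z₂| < 1.96) under a bivariate normal:

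| r | 0 | 0.3 | 0.5 | 0.7 | 0.77 | 0.8 | 0.9 |
|---|---|---|---|---|---|---|---|
| Rate | 9.75% | 9.5% | 9.1% | 8.3% | 8.0% | 7.8% | 7.0% |

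**4. Success on either the group or the group-by-time effect of either subscale.** Four independent tests: 1 − 0.95⁴ = 18.5%. Simulating the 2 × 5 mixed ANOVA under the null (20,000 runs, 16 per arm) gives 15–18% for subscale correlations from 0.8 down to 0. If only one score is analysed but either effect may count, the simulation gives 9.2–9.7%. If any of the ten subscale-by-time comparisons may count, it gives 25–31%.

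**5. Both subscales required.** The rate cannot exceed that of one test, so it is at most 5%. With no effect on either subscale, the simulation gives 0.2–2% for correlations 0 to 0.8.

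**6. Cost of control.**
- *Stated inputs, taken as describing a subscale.* At alpha 0.025, power is 98.8%, against 99.5% at 0.05: a loss of 0.7 points. Holm loses less, because once one subscale passes at 0.025 the other is tested at 0.05.
- *Weaker effect.* With 16 per arm, d = 1.02 gives 80% power at 0.05. A flat 0.025 lowers this to 70.3%. Holm, with the same effect on both subscales (simulated, 200,000 runs), gives 77.1%, 76.2%, 75.7% and 74.6% at r = 0, 0.5, 0.7 and 0.9. The loss is about 3–4 points up to r = 0.7 and 5.5 at 0.9.
- *Requiring both.* At 80% power each, the chance that both succeed is 0.80² = 64% if independent, and 69% at r = 0.5 (simulated).

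**The case against.** The strongest reply has three parts.

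**The plan does not say that each subscale is tested at 0.05, or that a hit on either would count.** This stands. A reader might infer a primary analysis with a known 8–10% error rate, but the documents do not support that. The alpha appears only in the power calculation, the analysis paragraph speaks of one outcome, and no success rule is given. The 8–10% is the consequence of one possible rule; another rule, both subscales required, keeps the rate at or below 5%. What survives is the absence of any rule. The single-outcome reading does not remove the problem either. It conflicts with the two outcomes in B3.A and still leaves two ANOVA effects open.

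**This is a 32-patient pilot, where formal familywise control is partly a matter of preference.** This has some weight, and Holm is only one valid choice. But B1 sets out to determine effectiveness, and B3.B powers a two-sided hypothesis test. Small size may excuse low power; it does not explain leaving the deciding test unnamed.

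**Control is not free.** This also stands. A reader might infer from the stated inputs that there is no trade-off. Those inputs put power near its ceiling and do not identify the score. With an effect that gives only 80% power, the loss is several points.

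**Conclusion.** The point holds as a gap in definition with a bounded numerical consequence. B3.A and the two parts of B3.B disagree or are silent on the score, the effect and the success rule, so nothing in the plan holds the primary claim at 5%.

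The size depends on the rule eventually used:
- Either subscale at 0.05: about 8–10% for correlations from 0 to about 0.77, and 7% at 0.9.
- Either ANOVA effect of either subscale: up to 18.5%, the value for four independent tests.
- Both subscales required, or a single score and effect (or a testing order) fixed in advance: at most 5%. The plan states none of these.

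The correlations are assumptions, as the documents give none. No single percentage can be called the trial's actual error rate.

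**What to change.** Before unblinding, amend the analysis paragraph of B3.B and bring B3.A (Outcome) and the power calculation into line with it:

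1. State which PANSS score or scores are primary, and which score the 10 points and SD 6 describe.
2. Name one deciding SNP-minus-placebo contrast, the same for both subscales, such as the difference in change at one named time.
3. Apply Holm across the two subscales at overall two-sided 0.05: the smaller p-value against 0.025 and, if it passes, the other against 0.05. Alternatively, state that both must be significant at 0.05.
4. Label all other time points and ANOVA effects as supportive.

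This takes a few sentences and changes no patients, visits or procedures. The price is power. Under Holm it is below 1 percentage point per subscale on the stated inputs, if they describe a subscale. It is about 3–4 points if the true effect gives only 80% power and is equal on both subscales, rising to 5.5 at correlation 0.9. Requiring both avoids splitting alpha but lowers the chance of overall success more in that weaker case (64–69% for correlations 0 to 0.5).

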Visits will consist of informed consent signing, inclusion/exclusion criteria review, medical record review, and psychiatric diagnostic assessments. Some of these assessments will be performed virtually. Medical clearance will also be performed and includes a review of concomitant medications, urine pregnancy and drug testing, blood collection for laboratory testing, electrocardiogram, and vital sign monitoring. Safety measures will also be performed, and they include the SAFTEE-SI, AIMS, and C-SSR.

Protocol for Nitroprusside Infusion

Protocol created with reference to BIDMCs Nitroprusside IV Drug Administration Guideline (Approved by Critical Care Practice, Critical Care Exec, Pharmacy and Therapeutics Committee on December 2005 and revised in February 2019) with amendments from the CRC and [name], as well as from the Critical Care Practice and Critical Care Executive Committees.

Scheduling:

 Participants will be scheduled for the single SNP infusion when CRC staff and PIs ([name] and [name]) are all available on site

 We will follow BIDMC guidelines, as well as our study staff and CRC recommendations for decision on pausing the study due to COVID19 restrictions

Infusion Monitoring:

- Pre-infusion orders
 - Semi-recumbent position, IV-line placement, Volumetric pump with a carrier line
 - nicotine patch [if appropriate, see cigarettes per day (cpd) break down below]
 - if 15 cpd: 21 mg patch
 - if 8-15 cpd: 14 mg patch
 - if 5-8 cpd: 7 mg patch
 - if <5 cpd: PRN nicotine gum or lozenges 2 mg (1 piece every 3-4 hours)
- 12-lead EKG
 - Pre-infusion (60 mins before)
 - During (30 mins after start of infusion)
 - Post-infusion (60 after end of infusion)
- VS (BP, HR, O2 sat)
 - Pre-infusion (baseline)
 - During
 - Phase I (q5 Xs 10 mins)
 - Phase II (q5min Xs 10 mins, then q10min Xs 40 mins, then q20min Xs 3 hours)
 - Post-infusion (q20mins Xs 60 mins)
- Study Investigators
 - Co-I: [name] will be present 30 minutes prior to SNP infusion
 - PI: [name] will be present during the entire study visit

Phase I Infusion Protocol

- Co-I ([name]) will be present during Phase I (10 mins)
- A 10-minute run-in period at 0.25 mcg/kg/min using a carrier line and infusion pump
- If SBP < 89 and/or if SBP decreased by >20% PAUSE infusion. Lie flat, feet up, call PIs
- If HR > 120 bpm and/or >20 bpm over baseline HR, PAUSE infusion. Lie flat, feet up, call PIs Continue to check BP.
- If SpO2 <92%, PAUSE infusion. Lie flat, feet up, call PIs

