- If patient reports headache, ask: "do you feel this headache is tolerable?"
 - If patient says "yes," continue dose
 - If patient says "no," PAUSE infusion. Call PIs
- If patient experiences symptomatic hypotension (nausea, dizziness) PAUSE infusion. Call Pls
- If Phase I is tolerated per the above guidelines after the 10-minute run-in period, then start Phase II

Phase II Infusion Protocol

- Co-I ([name]) will be present for the first 20 mins of Phase II to ensure safe up titration of SNP
- Increase to max dose of 0.5 mcg/kg/min with the following parameters
- If SBP between 81 and 89 and/or if SBP decreased by >20%, lower dose to Phase I dose for 15 min. Monitor with CRC Nurse.
 - If SBP rises to >89mm Hg continue Phase I dose
 - If SBP remains between 81 and 89mm Hg PAUSE and call PIs
 - If SBP <80, PAUSE infusion, lie flat, feet up & call PIs

- If HR >120 bpm and/or >20 bpm over baseline HR, lower dose to Phase I dose for 15 min.
 Continue to check BP
- If SpO2 < 92% PAUSE infusion and call PIs
- If patient reports headache, ask, "Do you feel this headache is tolerable?"
 - If patient says "yes", continue dose
 - If patient says "no", lower dose to Phase I dose for 15 min
 - If better, continue Phase I dose
 - If still intolerable, PAUSE infusion. Lie flat, feet up, call PIs
- If patient experiences symptomatic hypotension (nausea, dizziness) lower dose to Phase I dose for 15 min
 - If better, continue Phase I dose
 - If not, PAUSE infusion and call PIs

PRN Rescue Medications

- In consultation with CRC Nurse and study PIs
- Omnicell automated medication dispensing cabinet system available for dispensing rescue medication
- For SBP <80 mmHg, may give 250 ml 0.9% NS IV bolus via Sigma pump @999 ml/hr over 15 min X 2
- For rash may give Diphenhydramine 25 mg by mouth X 1
- The need for additional potential rescue medications to be available in the Omnicell will be discussed between study staff and pharmacy

Infusion Considerations

- IV line will be left in place for at least 1 hour.
- If additional IV medication is necessary, [name] and the CRC nurse will start the infusion and a medical team will be present during the entire infusion period.
- A study PI or Co-I will release the subject at the conclusion of the visit.
- A trained RA, research nurse, and study PI ([name]) will be present during the entire infusion and monitoring period.
- The psychiatry research staff member will administer rating scales.

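### Phase II infusion rules: after a heart-rate step-down no pause or onward dose is written, and a re-check systolic pressure of exactly 80 mmHg has no pause

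*Combined protocol and SAP*

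**What the plan says.** The rules are in B3.A, SNP Treatment Protocol. Phase I is described as "A 10-minute run-in period at 0.25 mcg/kg/min using a carrier line and infusion pump". Its heart-rate rule is "If HR > 120 bpm and/or >20 bpm over baseline HR, PAUSE infusion. Lie flat, feet up, call PIs".

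Phase II raises the rate to 0.5 mcg/kg/min. Its heart-rate rule uses the same limit: "If HR >120 bpm and/or >20 bpm over baseline HR, lower dose to Phase I dose for 15 min". The only words after it are "Continue to check BP".

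The neighbouring Phase II rules spell out what follows the step-down. For headache, the Phase I dose continues if the patient is better; otherwise "If still intolerable, PAUSE infusion. Lie flat, feet up, call PIs". For symptomatic hypotension, the Phase I dose continues if better; otherwise "If not, PAUSE infusion and call PIs". For systolic pressure the trigger is "If SBP between 81 and 89 and/or if SBP decreased by >20%, lower dose to Phase I dose for 15 min". At re-check, above 89 mmHg the Phase I dose continues, and from 81 to 89 the infusion is paused. A separate line pauses below 80. PRN Rescue Medications also sets the saline bolus at below 80.

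Vital signs in Phase II are taken on the schedule "Phase II (q5min Xs 10 mins, then q10min Xs 40 mins, then q20min Xs 3 hours". The exclusion criteria rule out a baseline systolic pressure under 100 mmHg.

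**The concern.** These rules decide whether a vasodilator infusion given outside an ICU continues, steps down or stops. B5 lists tachycardia and palpitations among the drug's side effects, so the heart-rate rule may well be used. The relative limit is also easy to reach: from an illustrative baseline of 70 bpm, 91 bpm meets it.

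Read literally, a heart rate that stays high in Phase II is never paused under the heart-rate rule, however high it goes, and that rule does not ask staff to call the investigators. Once heart rate settles, staff have to choose between staying at 0.25 and returning to 0.5 mcg/kg/min.

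The systolic rule has a smaller fault of the same kind. At re-check, a pressure of 80 gets a weaker response than 81.

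**Working it through.** The plan states no figure on this point, so the check compares the rules and counts the schedule.

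**Heart rate, side by side**

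| Rule | Dose when applied | If recovered | If not recovered |
|---|---|---|---|
| Phase I, heart rate | 0.25 | – | pause at once, call investigators |
| Phase II, systolic pressure | 0.5 to 0.25 for 15 min | stay at 0.25 | pause (except at 80, below) |
| Phase II, headache | 0.5 to 0.25 for 15 min | stay at 0.25 | pause |
| Phase II, symptomatic hypotension | 0.5 to 0.25 for 15 min | stay at 0.25 | pause |
| Phase II, heart rate | 0.5 to 0.25 for 15 min | not stated | no pause written |

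The heart-rate rule is the only Phase II step-down with neither exit.

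**When it can arise.** Infusion Monitoring gives 10/5 = 2 readings (minutes 5 and 10 of Phase II), then 40/10 = 4 (20 to 50), then 180/20 = 9 (70 to 230), 15 in all. The 15-minute step-down ends within the 230 minutes of Phase II for 14 of them, the last being 210 + 15 = 225. The critical-care co-investigator is written as present for the first 20 minutes of Phase II, and 12 of the 15 readings (30 to 230) come later. These counts describe the schedule; they are not event rates.

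**Dose at stake in the earliest case.** With a trigger at minute 5, the step-down ends at minute 20 and 230 − 20 = 210 minutes remain.

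- Heart rate settles: 210 × 0.25 = 52.5 mcg/kg, or 210 × 0.5 = 105 mcg/kg if the dose is raised again. The text does not choose.
- Heart rate stays high: the trigger is still met, which holds the dose at 0.25 and gives 52.5 mcg/kg. A pause that is not lifted gives 0.

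**Systolic pressure, re-check.** Checking whole numbers from 50 to 180 mmHg against the three branches (above 89, 81 to 89, below 80), the only value in none of them is 80. Fall = (baseline − reading)/baseline.

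- Baseline 101: (101 − 80)/101 = 20.8%. The rule for a fall above 20% still applies, but it only orders the dose already running. The same holds at every higher baseline.
- Baseline 100: (100 − 80)/100 = 20.0%, which is not above 20%, so no systolic rule applies.

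A participant with baseline 100 who is stepped down at 81 and reads 80 at re-check has no systolic instruction; had the reading stayed at 81, the infusion would be paused.

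**Systolic pressure, first reading at baseline 100.** 81 (19.0% fall) is in the 81–89 band and triggers step-down. 80 (20.0%) triggers nothing. 79 (21.0%) means pause. At baselines of 101 or more, a first reading of 80 does trigger step-down.

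**The case against.** The strongest reply is that the heart-rate rule is a standing condition. If heart rate is still above the limit after 15 minutes, the trigger is met again and the dose stays at 0.25 mcg/kg/min. That stands. A reader might infer that staff could go back to 0.5 while heart rate is high, and the text does not support that. What remains is the absent pause and the unstated dose after recovery.

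A second reply is that the softer response may be deliberate. Phase I is a tolerance run-in, Phase II is graded, the limit is low, and the critical-care committees amended and approved the protocol. This is possible, and it is why the clinical leads should confirm the limit. But the dose after recovery would still need stating.

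A third is that the Phase I rules resume once the Phase I dose does. The text restores only the dose. If the Phase I heart-rate rule were also back in force, a reading still above the limit would pause the infusion before the 15 minutes were up, leaving the waiting period no purpose. The neighbouring rules also write their own exits.

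A fourth is that supervision covers the gap. The PI is there throughout, nursing is 1:1, a critical-care physician is close by, and B5 promises continuous monitoring during the infusion. The text is called an outline and refers to a hospital guideline that is not included. All this lowers the risk, but nothing in the available text supplies the missing instructions.

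On systolic pressure, the objection that 80 is not wholly without action is right: for baselines of 101 or more the relative-fall rule keeps the lower dose running. The gap is 1 mmHg wide and looks like a boundary slip.

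**Conclusion.** The point holds for two defects. The heart-rate one matters more: the Phase II rule has no written escalation to a pause and no stated dose after recovery, and in the earliest case each leaves up to 52.5 mcg/kg undetermined. The systolic one is a one-value threshold error: 80 at re-check for every eligible baseline, and 80 as a first reading only at a baseline of exactly 100. The sponsor should correct both. The risk to participants is limited by the supervision described and by the other pressure, oxygen-saturation and symptom rules.

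The figures assume whole-number pressures, action at scheduled readings, a pause that is not lifted, and a pre-infusion baseline equal to the eligibility value. If a pre-infusion reading below 100 were accepted, a first reading of 80 would be missed there too, since (b − 80)/b is at most 20% whenever b is 100 or less.

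Three wider readings are not supported:

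- A reader might see a conflict between 60 minutes of scheduled post-infusion readings and 2 hours of recording. Both can be followed, and the flow chart that sets vital-sign times is not in the available text.
- A reader might fault the above-89 exit for not re-testing the relative fall. It has a stated action, and adding a relative test is a clinical choice.
- A reader might infer a loss of power or a bias in the PANSS analysis. Nothing here shows either.

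**What to change.** In the Phase II Infusion Protocol, add after the heart-rate step-down: *if heart rate is back within limits, continue the Phase I dose; if still above the limit after 15 minutes, pause and call the investigators.* This matches the headache and symptomatic-hypotension rules. The clinical leads should confirm that the limit is the one they want as a ground for pausing; if they intend no pause, the protocol should say so and state the dose to continue.

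Change below 80 mmHg to 80 mmHg or below in both the Phase II pause rule and the rescue-fluid rule.

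The cost is a short amendment and a revised nursing order sheet. The real downside is that some participants with normal blood pressure may have the infusion paused and lose dose: up to 52.5 mcg/kg each in the earliest case, compared with staying at 0.25. The documents give no heart-rate data from which to estimate how many.
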